4.7 Efficacy variables

For each efficacy assessment, study day will be calculated as: the date of assessment – the date of first dose of study drug + 1. As deviations are expected in the number of days from the date of first dose (i.e., study day 1) to the study day that planned assessments actually occur, visit windows will be used to derive visit numbers for use in efficacy analyses. Efficacy variable visit windows and their associated derived visit numbers and labels are defined in Table 2.

Derived visit number	Derived visit label	Visit window (days)
1	Visit 1	≤-1
2	Visit 2 (Week 0)	0
3	Visit 3 (Week 1)	1 to 11
4	Visit 4 (Week 2)	12 to 18
5	Visit 5 (Week 3)	19 to 25
6	Visit 6 (Week 4)	26 to 32
7	Visit 7 (Week 5)	33 to 39
8	Visit 8 (Week 6)	40 to 50

 Table 2: Visit windows for efficacy variables

For all efficacy variables, baseline will be defined as the last assessment prior to the first dose of IP. Change from baseline values will be calculated as the assessment value minus the baseline value. For the derivation of any total or subscale score, if at least 80% of the items needed to calculate a score have valid responses, then that score will be computed as the sum of all non-missing items divided by the percentage of non-missing items in that scale or subscale. If fewer than 80% of the items have valid responses, then that score will be considered as missing.

For some efficacy variables, the last observation carried forward (LOCF) method of imputation will be used to calculate additional LOCF efficacy variables. For LOCF variables, a derived visit number of 99 and a visit label of "LOCF" will be assigned.

4.7.1 Attention Deficit Hyperactivity Disorder Rating Scale Version 5

The Attention Deficit Hyperactivity Disorder Rating Scale Version 5 (ADHD-RS-5; DuPaul et al., 2016) is a parent reported/clinician-rated scale designed to reflect the symptomatology of ADHD based on the Diagnostic and Statistical Manual of Mental Disorders, Fifth Edition (DSM-5) criteria. The ADHD-RS-5 is comprised of 18 frequency items and 12 impairment items. Each frequency item will be scored on a scale from 0 = "Never or rarely" to 3 = "Very often". Each impairment item will be scored on a scale from 0 = "No Problem" to 3 = "Severe Problem". Each ADHD-RS-5 item score will be recorded in the eCRF.

4.7.1.1 ADHD-RS-5 total score

The ADHD-RS-5 total score will be calculated as the sum of the 18 frequency item scores. The total score ranges from 0 to 54. Higher scores indicate greater symptom severity.

The change from baseline in the ADHD-RS-5 total score is the primary efficacy variable and will be calculated at each post-baseline timepoint. In addition, the percent reduction in ADHD-RS-5 total score will be calculated at each post-baseline timepoint as the change from baseline value divided by the baseline value.

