4.7.1.2 ADHD-RS-5 response

An indicator of ADHD-RS-5 response will be calculated at each post-baseline timepoint as:

- IF the percent reduction in ADHD-RS-5 total score is ≥30%, THEN set the ADHD-RS-5 response indicator equal to 1.
- IF the percent reduction in ADHD-RS-5 total score is < 30%, THEN set the ADHD-RS-5 response indicator equal to 0.

In addition to deriving ADHD-RS-5 response at each timepoint, an LOCF ADHD-RS-5 response indicator will be calculated.

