4.7.3 Combined ADHD-RS-5/CGI-I response and remission

4.7.3.1 Combined ADHD-RS-5/CGI-I response

An indicator of combined ADHD-RS-5/CGI-I response will be calculated as:

- IF the percent reduction in ADHD-RS-5 total score is ≥30% AND the CGI-I score is ≤2 (i.e., "very much improved" or "much improved"), THEN set the combined ADHD-RS-5/CGI-I response indicator equal to 1.
- OTHERWISE, set the ADHD-RS-5/CGI-I response indicator equal to 0.

In addition to deriving combined response at each timepoint, an LOCF combined ADHD-RS-5/CGI-I response indicator will be calculated.

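### As written, the SAP's percent-reduction formula has the wrong sign: only subjects whose ADHD-RS-5 score worsens by 30% or more are coded as responders

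*SAP*

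**What the plan says.** SAP 4.7 sets one rule for every efficacy variable: "Change from baseline values will be calculated as the assessment value minus the baseline value". SAP 4.7.1.1 gives the range and direction of the primary scale: "The total score ranges from 0 to 54" and "Higher scores indicate greater symptom severity". The same section derives the percent reduction in total score at each post-baseline timepoint "as the change from baseline value divided by the baseline value".

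SAP 4.7.1.2 turns that quantity into an indicator with two rules: "IF the percent reduction in ADHD-RS-5 total score is ≥30%, THEN set the ADHD-RS-5 response indicator equal to 1" and "IF the percent reduction in ADHD-RS-5 total score is < 30%, THEN set the ADHD-RS-5 response indicator equal to 0". SAP 4.7.3.1 uses the same quantity for the combined ADHD-RS-5/CGI-I response. That indicator is 1 only if the percent reduction is at least 30% and the CGI-I score is 2 or lower; for all other cases the instruction is "OTHERWISE, set the ADHD-RS-5/CGI-I response indicator equal to 0".

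SAP 5.4 analyses the LOCF versions of both indicators by logistic regression in the full analysis set, reporting odds ratios, confidence intervals and p-values. It also calls for descriptive summaries of the response indicators by treatment group and derived visit. The objectives in SAP 2.1.2 and Protocol Section 7, and the endpoint definitions in Protocol 14.1.1, all describe ADHD-RS-5 response as a fall of at least 30% from baseline. SAP 6.1 records no change from the protocol's analyses.

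**The concern.** Because change is assessment minus baseline and higher scores are worse, a subject who improves has a negative change. Dividing by a positive baseline keeps the sign negative. The variable called percent reduction is therefore negative for everyone who improves and positive for everyone who worsens, and the 30% threshold is applied to the wrong side of zero.

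Two of the three response endpoints depend on this variable: ADHD-RS-5 response and combined response. Under literal programming, the odds ratio for ADHD-RS-5 response would compare the arms on rates of worsening. The combined indicator would require a worsening of at least 30% in a subject whom the clinician rates as much or very much improved.

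These endpoints carry weight in this programme. Protocol 6.1 and 6.2 report that the earlier placebo-controlled adolescent trial missed its primary efficacy objective but showed significant differences on all three response criteria. A reader would look at the same criteria here.

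**Working it through.** The plan states no numerical result on this point, so there is no figure to reproduce. The check applies the written rule and the sign-corrected rule to the same scores.

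**Inputs**
- Change = assessment − baseline (SAP 4.7).
- Total score runs from 0 to 54, higher is worse (SAP 4.7.1.1).
- Response = 1 at 30% or more, 0 below 30% (SAP 4.7.1.2).
- Baseline score at least 28 (Protocol 8.5.1, inclusion criterion 5).
- ADHD-RS-5 remission is a score of 18 or lower (SAP 4.7.1.3).

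**Formulas**, with b = baseline and x = assessment
- As written: 100 × (x − b) / b
- Sign-corrected: 100 × (b − x) / b

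**Worked cases**

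| Baseline → assessment | As written | Coded | Sign-corrected | Coded |
|---|---|---|---|---|
| 40 → 24 | −40.0% | 0 | +40.0% | 1 |
| 40 → 28 | −30.0% | 0 | +30.0% | 1 |
| 40 → 30 | −25.0% | 0 | +25.0% | 0 |
| 28 → 18 | −35.7% | 0 | +35.7% | 1 |
| 30 → 40 | +33.3% | 1 | −33.3% | 0 |
| 40 → 52 | +30.0% | 1 | −30.0% | 0 |
| 41 → 54 | +31.7% | 1 | −31.7% | 0 |
| 42 → 54 | +28.6% | 0 | −28.6% | 0 |

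**All possible whole-number scores.** Baselines 28 to 54 give 27 values and assessments 0 to 54 give 55, so there are 27 × 55 = 1,485 pairs.
- As written, 136 pairs are coded as response, and every one is a worsening.
- Sign-corrected, 790 pairs are coded as response, and every one is an improvement.
- No pair is a response under both rules.
- There are 27 × 19 = 513 pairs that end in remission (0 to 18). None is a response as written. Under the corrected rule all 513 are, because even the smallest such fall, 28 to 18, is 35.7%.

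These are counts of possible score pairs, not forecasts of how many subjects would fall in each cell.

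**Ceiling.** A 30% rise must stay at or below 54, so b ≤ 54 / 1.3 = 41.5. As written, a subject with a baseline of 42 or more could never be coded a responder.

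**Combined response.** As written, coding 1 needs x ≥ 1.3 × b together with CGI-I of 2 or lower. These two conditions point in opposite clinical directions, so the indicator should be close to zero in both arms. This last step is a judgement, not a calculation.

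**The case against.** The strongest reply is that the intent cannot be mistaken. The variable is named a reduction, and the objectives and protocol define response as a reduction. The protocol also uses the word change loosely: Section 6.1 gives the earlier trial's criterion as a reduction and Section 6.2 gives the same criterion as a change. A competent programmer would probably correct the sign. A literal coding would also show up in the by-visit summaries, where every subject in ADHD-RS-5 remission would appear as a non-responder. The documents do not show how the variable was programmed.

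The scope is limited too. The formula does not touch the primary MMRM on change from baseline, CGI-I response (the key secondary endpoint), any of the remission indicators, CGI-S or the Conners scales. The two affected endpoints are additional secondary endpoints, for which SAP 5.4 makes no multiplicity correction. Nor is the effect an exact reversal: subjects who move by less than 30% in either direction are coded 0 under both rules.

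All of this stands, and it limits how far the error reaches. It does not make the derivation right. A program that matches the SAP gives wrong results, and a program that gives right results departs from the SAP without a record. Labels nearby cannot be relied on to settle the matter either: SAP 4.7.2.1 and 4.7.2.2 each assign a value to an indicator other than the one being defined. I found no sentence in either document that reverses the sign.

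**Conclusion.** The concern holds for the text as written. Taken together, SAP 4.7, 4.7.1.1 and 4.7.1.2 code as ADHD-RS-5 responders only subjects who worsen by at least 30%, and only those with a baseline of 41 or less. Every subject who truly meets the ADHD-RS-5 or combined response criterion is coded 0. One planned secondary endpoint would measure worsening and another would be almost empty.

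This conclusion assumes literal execution of the SAP. It makes no claim about the code actually used, and it does not extend to the primary or key secondary analyses. The correction should be made despite the limited scope, because the faulty sentence is the operative derivation for two inferential analyses.

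**What to change.** In SAP 4.7.1.1, define percent reduction as 100 × (baseline − assessment) / baseline, which equals −100 × change / baseline. This also supplies the missing factor of 100, so that the scale matches the 30% threshold. Leave the threshold rules in 4.7.1.2 and 4.7.3.1 as they are.

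Check the analysis program against the corrected line with two test cases: 40 → 24 must give +40% and response 1, and 30 → 40 must give −33.3% and response 0. If the SAP is already final, record the correction in the clinical study report, as SAP Section 1 provides for changes. Carry the corrected definition into the separate Part B SAP.

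The cost is one line of text and a short program check. Data collection, sample size and design do not change.

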4.7.1.2 ADHD-RS-5 response

An indicator of ADHD-RS-5 response will be calculated at each post-baseline timepoint as:

- IF the percent reduction in ADHD-RS-5 total score is ≥30%, THEN set the ADHD-RS-5 response indicator equal to 1.
- IF the percent reduction in ADHD-RS-5 total score is < 30%, THEN set the ADHD-RS-5 response indicator equal to 0.

In addition to deriving ADHD-RS-5 response at each timepoint, an LOCF ADHD-RS-5 response indicator will be calculated.

4.7.1.3 ADHD-RS-5 remission

An indicator of ADHD-RS-5 remission will be calculated at each post-baseline timepoint as:

- IF the ADHD-RS-5 total score is \leq 18, THEN set the ADHD-RS-5 remission indicator equal to 1.
- IF the ADHD-RS-5 total score is >18, THEN set the ADHD-RS-5 remission indicator equal to 0.

In addition to deriving ADHD-RS-5 remission at each timepoint, an LOCF ADHD-RS-5 remission indicator will be calculated.

4.7.1.4 ADHD-RS-5 Inattention subscale score

The ADHD-RS-5 Inattention subscale score will be calculated as the sum of the first 9 individual item scores. The Inattention subscale score ranges from 0 to 27. Higher scores indicate greater symptom severity. The change from baseline in ADHD-RS-5 Inattention subscale score will be calculated at each post-baseline timepoint.

4.7.1.5 ADHD-RS-5 Hyperactivity–Impulsivity subscale score

The ADHD-RS-5 Hyperactivity–Impulsivity subscale score will be calculated as the sum of the next 9 individual item scores (i.e., from items 10 to 18). The Hyperactivity–Impulsivity subscale score ranges from 0 to 27. Higher scores indicate greater symptom severity. The change from baseline in ADHD-RS-5 Hyperactivity–Impulsivity subscale score will be calculated at each post-baseline timepoint.

4.7.2 Clinical Global Impression

The Clinical Global Impression (CGI; Guy, 1976) scale is a clinician-rated scale consisting of 3 items. Only the CGI – Severity (CGI-S) and CGI – Improvement (CGI-I) items will be assessed in this study. The CGI-S item is rated on a 7-point scale from 1 = "Normal, not at all ill" to 7 = "Among the most severely ill patients". The CGI-I item is rated

on a 7-point scale from 1 = "Very much improved" to 7 = "Very much worse". Each CGI item score will be recorded in the eCRF.

A CGI-S or CGI-I score of "0" will be considered as missing as this score denotes "Not assessed".

4.7.2.1 CGI-I response

An indicator of CGI-I response will be calculated as:

- IF the CGI-I score is ≤2 (i.e., "very much improved" or "much improved"), THEN set the CGI-I response indicator equal to 1.
- IF the CGI-I score is >2, THEN set the ADHD-RS-5 response indicator equal to 0.

In addition to deriving CGI-I response at each timepoint, an LOCF CGI-I response indicator will be calculated.

4.7.2.2 CGI-I remission

An indicator of CGI-I remission will be calculated as:

- IF the CGI-I score is equal to 1 (i.e., "very much improved"), THEN set the CGI-I response indicator equal to 1.
- IF the CGI-I score is >1, THEN set the CGI-I response indicator equal to 0.

In addition to deriving CGI-I remission at each timepoint, an LOCF CGI-I remission indicator will be calculated.

4.7.2.3 CGI-S score

The change from baseline in CGI-S will be calculated at each post-baseline timepoint.

4.7.3 Combined ADHD-RS-5/CGI-I response and remission

4.7.3.1 Combined ADHD-RS-5/CGI-I response

An indicator of combined ADHD-RS-5/CGI-I response will be calculated as:

- IF the percent reduction in ADHD-RS-5 total score is ≥30% AND the CGI-I score is ≤2 (i.e., "very much improved" or "much improved"), THEN set the combined ADHD-RS-5/CGI-I response indicator equal to 1.
- OTHERWISE, set the ADHD-RS-5/CGI-I response indicator equal to 0.

In addition to deriving combined response at each timepoint, an LOCF combined ADHD-RS-5/CGI-I response indicator will be calculated.

4.7.3.2 Combined ADHD-RS-5/CGI-I remission

An indicator of combined ADHD-RS-5/CGI-I remission will be calculated as:

- IF the ADHD-RS-5 total score is \leq 18 AND the CGI-I score is equal to 1 (i.e., "very much improved"), THEN set the combined ADHD-RS-5/CGI-I remission indicator equal to 1.
- OTHERWISE, set the combined ADHD-RS-5/CGI-I remission indicator equal to 0.

In addition to deriving combined remission at each timepoint, an LOCF combined ADHD-RS-5/CGI-I remission indicator will be calculated.

4.7.4 Conners 3rd Edition – Parent Short Form

The Conners 3rd Edition – Parent Short Form [Conners 3-P(S); Conners, 2008] is a parent completed assessment consisting of 45 items to assess the severity of ADHD and other common co-morbid disorders in children and adolescents aged 6 to 18 years. Only the 43 multiple choice items will be assessed in this study (i.e., the final two open ended questions will not be assessed). The Conners 3-P(S) consists of 6 content subscales: Inattention, Hyperactivity/Impulsivity, Learning Problems, Executive Functioning, Aggression, and Peer Relations. Each item from these content subscales will be scored on a scale from 0 = "Not true at all (Never, Seldom)" to 3 = "Very much true (Very often, Very Frequently)". Additional Positive Impression and Negative Impression items will be scored on a scale from 0 to 1. Each Conners 3-P(S) item score will be recorded in the eCRF.

4.7.4.1 Conners 3-P(S) Inattention subscale score

The Conners 3-P(S) Inattention subscale score will be calculated as the sum of the item 17, item 27, item 30, item 34, and item 41 scores. The Inattention subscale score ranges from 0 to 15. Higher scores indicate greater symptom severity. The change from baseline score will be calculated at each applicable post-baseline timepoint.

4.7.4.2 Conners 3-P(S) Hyperactivity/Impulsivity subscale score

The Conners 3-P(S) Hyperactivity/Impulsivity subscale score will be calculated as the sum of the item 3, item 5, item 7, item 13, item 24, and item 28 scores. The Hyperactivity/Impulsivity subscale score ranges from 0 to 18. Higher scores indicate greater symptom severity. The change from baseline score will be calculated at each applicable post-baseline timepoint.

4.7.4.3 Conners 3-P(S) Learning Problems subscale score

The Conners 3-P(S) Learning Problems subscale score will be calculated as the sum of the item 8, item 10, item 25, item 36, and item 39 scores. The Learning Problems subscale score ranges from 0 to 15. Higher scores indicate greater symptom severity. The change from baseline score will be calculated at each applicable post-baseline timepoint.

4.7.4.4 Conners 3-P(S) Executive Functioning subscale score

The Conners 3-P(S) Executive Functioning subscale score will be calculated as the sum of the item 1, item 15, item 20, item 32, and item 35 scores. The Executive Functioning subscale score ranges from 0 to 15. Higher scores indicate greater symptom severity. The change from baseline score will be calculated at each applicable post-baseline timepoint.

4.7.4.5 Conners 3-P(S) Aggression subscale score

The Conners 3-P(S) Aggression subscale score will be calculated as the sum of the item 14, item 19, item 21, item 23, and item 26 scores. The Aggression subscale score ranges from 0 to 15. Higher scores indicate greater symptom severity. The change from baseline score will be calculated at each applicable post-baseline timepoint.

4.7.4.6 Conners 3-P(S) Peer Relations subscale score

The Conners 3-P(S) Peer Relations subscale score will be calculated as the sum of the item 4, item 6, item 18, item 38, and item 43 scores. The Peer Relations subscale score ranges from 0 to 15. Higher scores indicate greater symptom severity. The change from baseline score will be calculated at each applicable post-baseline timepoint.

4.8 Safety variables

For all safety variables, baseline will be defined as the last assessment prior to the first dose of IP. Change from baseline values will be calculated as the assessment value minus the baseline value. For each safety assessment, study day will be calculated as: the date of assessment – the date of first dose + 1.

4.8.1 Adverse events

An adverse event (AE) is defined as any untoward medical occurrence in a patient or clinical investigation subject administered a pharmaceutical product that does not necessarily have a causal relationship with the product. An

AE can therefore be any unfavorable and unintended sign (including a new, clinically important abnormal laboratory finding), symptom, or disease, temporally associated with the product, whether related to the product.

AEs are collected from the time of the informed consent is signed until the follow-up call is completed. For each AE, the following data will be recorded in the eCRF: verbatim text, start date, stop date, outcome, investigator's assessment of severity, assessment of seriousness, relationship to IP, action taken with IP, and discontinuation due to AE. The verbatim text will be coded by using Medical Dictionary for Regulatory Affairs (MedDRA) version 19.

- Outcome will be recorded as "FATAL"; "NOT RECOVERED/NOT RESOLVED"; "RECOVERED/RESOLVED"; "RECOVERED/RESOLVED WITH SEQUELAE"; "RECOVERING/RESOLVING"; or "UNKNOWN".
- Investigator's assessment of severity will be recorded as "MILD"; "MODERATE"; or "SEVERE".
- Assessment of seriousness will be recorded as "N" or "Y".
- Relationship to IP will be recorded as "NOT RELATED"; "POSSIBLY RELATED"; or "PROBABLY RE-LATED".
- Action taken with IP will be recorded as "DOSE NOT CHANGED"; "DRUG WITHDRAWN"; "NOT APPLI-CABLE"; "UNKNOWN"; "DOSE INCREASED"; "DOSE REDUCED"; or "DRUG INTERRUPTED".
- Discontinuation due to AE will be recorded as "N" or "Y".

A flag for related AEs will be calculated as:

- IF the relationship to IP is "POSSIBLY RELATED" or "PROBABLY RELATED", THEN set the related AE flag equal to "Y".
- OTHERWISE, set the related AE flag equal to "N".

A flag for AEs leading to study drug withdrawal will be calculated as:

- IF the action taken with IP is "DRUG WITHDRAWN", THEN set the AE leading to study drug withdrawal flag equal to "Y".
- OTHERWISE, set the AE leading to study drug withdrawal flag equal to "N".

Treatment emergent AEs (TEAEs) are defined as those AEs occurring or worsening after the first dose of IP and within 3 days of the last dose of IP. If an AE start date is completely missing (i.e., in which the day, month, and year are all unknown), then the AE start date will be set to the date of first dose of IP. For a partial AE start date, the following conventions will be used for imputing the AE start date:

- When the year is present and the month and day are missing:
 - If the year of AE start = the year of first dose of IP, then the month and day will be set to the month and day of first dose of IP.
 - If the year of AE start < the year of first dose of IP, then the month and day will be set to December 31st.
 - If the year of AE start > the year of first dose of IP, then month and day will be set to January 1st.
- When the year and day are present and the month is missing:
 - If the year of AE start = the year of first dose of IP, then the month will be set to the month of first dose of IP.
 - If the year of AE start < the year of first dose of IP, then the month will be set to December.
 - If the year of AE start > the year of first dose of IP, then the month will be set to January.
- When the month and year are present and the day is missing:
 - If the year of AE start = the year of first dose of IP and

- \circ the month of AE start = the month of first dose of IP, then the day will be set to the day of first dose of IP.
- \circ the month of AE start < the month of first dose of IP, then the day will be set to the last day of the month.
- $\circ\,$ the month of AE start > the month of first dose of IP, then the day will be set to the 1st day of the month.
- If the year of AE start < the year of first dose of IP, then the day will be set to the last day of the month.
- If the year of AE start > the year of first dose of IP, then the day will be set to the 1st day of the month.
- If the imputed AE start date is after the AE stop date, then the AE start date will be set to the AE stop date.

For each AE, a treatment emergent flag will be calculated using the recorded AE start date (or imputed start date, where applicable).

• IF the date of first dose of IP \leq AE start date \leq date of last dose of IP + 72 hours, THEN set the treatment emergent flag equal to "Y".

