### 9.7 Dose Adjustment Criteria

The duration of the dose-optimization phase is 4 weeks to allow for weekly titration up to the highest dose and 1 titration down to the previous dose, if necessary.

Following enrollment, all subjects will begin taking AEVI-001 or placebo and will be evaluated after approximately 7 days ( $\pm$  2 days) for safety and efficacy. Subjects may be titrated weekly to the next available dose strength after approximately 7 days ( $\pm$  2 days) on the previous dose, based on the overall response of the subject. Additionally, if needed, a subject may be down-titrated once to the previous dose level to optimize tolerability and efficacy. Subjects unable to tolerate the lowest available dose (100 mg twice daily or placebo) will be discontinued from the study. Subject response will be categorized by the investigator as 1 of 3 conditions and associated actions, with titration continuing until an "acceptable response" is achieved:

□ Intolerable response (i.e., intolerable side effects): Requires the subject to be tapered to a lower dose of AEVI-001 or placebo (if available). However, if this lower dose produces an intolerable response as well, the subject should be discontinued from the study.
 □ Ineffective response: Subject has not achieved a CGI-I score of <3. This response requires increasing titration of AEVI-001 or placebo to the next available dose strength, provided tolerability is acceptable, followed by weekly evaluation.

 □ Acceptable response: A response is defined as acceptable if it shows a significant reduction in symptoms, defined by a CGI-I score of <3, with tolerable side effects. Subjects categorized as "acceptable" may be maintained at their current dose of AEVI-001 or placebo for the remainder of the study. Subjects who are tolerating IP at the highest

available dose but do not achieve an acceptable response should be continued in the study.

If, in the opinion of the investigator, the "acceptable" dose is well tolerated and the subject would potentially receive additional symptom reduction, the dose may be increased to the next dosage strength.

If, in the opinion of the investigator, the subject experiences unacceptable tolerability, the dose of AEVI-001 or placebo may be reduced (if available) by 1 dose level (to the previous dose). If the subject tolerates the dose reduction and maintains symptom control, the subject may be maintained at that reduced dose for the remainder of the study.

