### 14.3.5.1 Adverse Events

Adverse events will be coded using the most recent version of the Medical Dictionary for Regulatory Affairs (MedDRA). The incidence of TEAEs will be summarized by treatment group, system organ class (SOC), and preferred term. An AE will be considered treatment emergent if it occurs after the first dose of IP and within 3 days after a subjects last dose of IP. Similar summaries will be produced for SAEs and AEs leading to discontinuation. The intensity of AEs and the relationship to investigational product will also be summarized for each SOC and preferred term.

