5.5.2 AEs

The overall incidence of subjects having at least one AE in each of the following categories will be summarized by treatment group:

- Any TEAE
- Any SAE
- Any AE leading to death
- Any TEAE leading to study drug withdrawal
- Any related TEAE

All AE data will be listed by subject. Separate listings by subject will presented for all SAEs, AEs leading to death, and TEAEs leading to study drug withdrawal.

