5.5.2.3 TEAEs leading to study drug withdrawal

The incidence of TEAEs leading to study drug withdrawal will be summarized by treatment group, SOC, and preferred term. Each subject will be counted only once per SOC and preferred term.

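### The SAP flags AE withdrawals from the action-taken code alone and leaves the recorded answer on discontinuation due to AE out of every summary, so the AE table can miss discontinuations that the protocol says will be summarized

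*SAP*

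**What the plan says.** SAP 4.8.1 lists the variables held for each adverse event. Action taken with study drug has seven codes: DOSE NOT CHANGED, DRUG WITHDRAWN, NOT APPLICABLE, UNKNOWN, DOSE INCREASED, DOSE REDUCED and DRUG INTERRUPTED. A second field stands beside it: "Discontinuation due to AE will be recorded as" N or Y.

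The withdrawal flag reads only the action code. If it is DRUG WITHDRAWN, "THEN set the AE leading to study drug withdrawal flag equal to" Y. For any other code, "OTHERWISE, set the AE leading to study drug withdrawal flag equal to" N.

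The flag defines three outputs: the overview row "Any TEAE leading to study drug withdrawal" and a separate listing, both in SAP 5.5.2, and the table in SAP 5.5.2.3, where "The incidence of TEAEs leading to study drug withdrawal will be summarized by treatment group, SOC, and preferred term".

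Protocol 14.3.5.1 names the quantity differently: "Similar summaries will be produced for SAEs and AEs leading to discontinuation". SAP 6.1 gives changes from the protocol's analyses as not applicable.

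Protocol 9.7 describes how intolerance is handled. Where a lower dose exists the dose is lowered first; then "if this lower dose produces an intolerable response as well, the subject should be discontinued from the study". Only one reduction is allowed, with no dose change after it.

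**The concern.** The variable that answers the protocol's question directly is the yes/no field. The SAP collects it, then bases the summary on a different field. The two should usually agree, but nothing in the SAP makes them agree or says what happens when they do not.

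The dose-adjustment scheme makes disagreement plausible. A subject above the lowest dose who stops for intolerance may first have had the dose lowered, so one event can have two actions in sequence. The SAP describes a single action value. Protocol 11.1.2 requires a new record when severity changes, but neither document says what to do when only the action changes, or whether the first or the last action is kept.

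At stake is the count, by arm and by type of event, of adverse events that ended participation. The outputs are descriptive, and no efficacy result or hypothesis test depends on them. In arms this small, however, one or two subjects change how the table reads.

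**Working it through.** The documents state no figure for this flag, so there is nothing to reproduce. The check applies the rule to every possible record and then scales the result to the planned arm sizes.

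**Step 1. Apply the SAP 4.8.1 rule.** Seven action codes times two discontinuation answers gives 14 combinations.

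| Action taken | Flag if discontinuation = N | Flag if discontinuation = Y |
|---|---|---|
| DRUG WITHDRAWN | Y | Y |
| DOSE REDUCED | N | **N (missed)** |
| DRUG INTERRUPTED | N | **N (missed)** |
| DOSE NOT CHANGED | N | **N (missed)** |
| DOSE INCREASED | N | **N (missed)** |
| NOT APPLICABLE | N | **N (missed)** |
| UNKNOWN | N | **N (missed)** |

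Of the seven combinations with discontinuation = Y, the rule captures one and misses six. The reverse disagreement, DRUG WITHDRAWN with N, is flagged. These are counts of possible codings, not expected frequencies.

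**Step 2. Trace where a missed event goes.**

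- Lost from: the SAP 5.5.2 overview row, the SAP 5.5.2.3 table and the withdrawal listing.
- Kept in: the listing of all AE data (SAP 5.5.2), and the disposition summary by arm (SAP 5.1.1) if the site chose Adverse Event as the reason (SAP 4.1).
- Not supplied by disposition: system organ class or preferred term. Protocol 8.7 also puts only one reason, the most clinically relevant, on the case report form, so the disposition count need not equal the AE count.

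**Step 3. Scale.** The SAP covers Part A only. SAP 2.3 plans 42 randomized subjects, possibly raised to 64. At 1:1 this is 42/2 = 21 or 64/2 = 32 per arm, taking every randomized subject as dosed and so in the safety set.

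- One subject: 1/21 = 4.8 percentage points; 1/32 = 3.1 points.
- Three subjects: 3/21 = 14.3 points; 3/32 = 9.4 points.

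The range of one to three affected subjects in an arm is an assumption to show scale. The documents give no count, and it could be zero.

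**Step 4. Apply the corrected rule.** With the flag set to Y when the action is DRUG WITHDRAWN or discontinuation is Y, all seven Y combinations are captured. DRUG WITHDRAWN with N stays flagged and needs a query.

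**The case against.** **The loss depends on site coding.** An event is missed only if the action code is never updated to DRUG WITHDRAWN and no new record is opened. The eCRF completion guidelines (Protocol 15.2.1) and the consistency checks in the data management plan (Protocol 15.3.2) may deal with this, and neither is available here. The route is also narrower than it may look: the intolerable response at the lower dose need not be the same event, a change in severity opens a new record, and subjects on the lowest dose stop without a reduction step. All of this stands, and it is why no frequency can be claimed. It does not remove the point: the SAP states a rule that gives N to a record answered Y, and the mismatch with the protocol's promised summary exists however sites code.

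**A reader might infer that these discontinuations disappear from the report, or that the reported rate would be halved.** The documents do not support either. The subject can still be counted under Adverse Event in disposition, and the event remains in the full AE listing. Any split between captured and missed discontinuations would be invented.

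**A reader might also infer that leaving out a count of dose reductions due to AEs is part of the error.** It is not. Protocol 14.3.5.1 promises no such count, and SAP 5.5.1.2 summarizes optimized dose and exposure by arm and lists all exposure data.

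**An either-field rule could import entry errors,** for example DOSE NOT CHANGED with Y, and the documents do not say whether the yes/no field means stopping the drug or leaving the study. This stands in part. It is a reason to query discordant records as well as change the rule, not a reason to leave the field unused.

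**Conclusion.** The point holds as a specification error with a conditional effect. What is certain from the text is that the flag reads the action code alone, that the discontinuation answer enters no derivation or summary, and that the SAP's table therefore rests on a different variable from the one matching the protocol's commitment, with no change declared.

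What is conditional is the undercount. It requires a record with discontinuation = Y and an action other than DRUG WITHDRAWN at database lock. Whether any such record will exist, and in which arm, cannot be told from the documents. Each affected subject would lower an arm's rate in the AE table by 4.8 percentage points at 21 per arm or 3.1 at 32. The overview row, the table by system organ class and preferred term, and one listing are exposed; disposition and the full AE listing are not. The change is worth making because it is nearly free and removes the dependence on an unstated coding habit.

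**What to change.** 1. In SAP 4.8.1, set the flag to Y if action taken is DRUG WITHDRAWN **or** discontinuation due to AE is Y; otherwise N.
2. Retitle the SAP 5.5.2 row, the 5.5.2.3 table and the listing as TEAEs leading to discontinuation, to match Protocol 14.3.5.1.
3. Before database lock and while still blinded, query every record where the action code, the discontinuation answer and the disposition reason disagree. State in the SAP or the completion guidelines which action is entered when an event had several, and whether the yes/no field refers to drug or study.

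Both fields are already collected, so the cost is a few lines of SAP text and programming. The one downside is a small number of discordant records to resolve. A further row for TEAEs leading to dose reduction could be added from the same action field, but it is optional and separate from this correction. None of this touches how subjects are dosed or managed.
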